7.5.3 Medication during Wash-out and Follow-up Period

The medication will also be summarized and listed for wash-out period and follow-up period overall. Washout Period will start on the day after the last dose date in Period 1 and end on the day before dosing in Period 2. Follow-up Period will start on the day after the last dose of study drug in the study.

7.6 STUDY DRUG EXPOSURE AND COMPLIANCE

Exposure to study drug (i.e., duration of treatment) will be summarized by treatment for the Part A FAS and the Part B FAS in terms of duration of treatment a subject received (in days), defined as:

- If a patient takes the first dose of study drug in the morning and the last dose of study drug in the afternoon, then exposure (days) will be defined as: last day of study drug - first day of study drug + 1
- If a patient takes the first dose of study drug in the morning and the last dose of study drug in the morning, then exposure (days) will be defined as: last day of study drug - first day of study drug + 0.5
- If a patient takes the first dose of study drug in the afternoon and the last dose of study drug in the morning, then exposure (days) will be defined as: last day of study drug - first day of study drug
- If a patient takes the first dose of study drug in the afternoon and the last dose of study drug in the afternoon, then exposure (days) will be defined as: last day of study drug - first day of study drug + 0.5

1006696
Parion Sciences Incorporated
CLEAN-PCD
SAP Version 1.0

Study drug compliance will be summarized by treatment based on Part A FAS and Part B FAS. Study drug compliance will be calculated for each treatment as follows:

$100 \times [(Total\ number\ of\ vials\ dispensed - the\ total\ number\ of\ unused\ vials\ returned - the\ total\ number\ of\ vials\ reported\ as\ lost\ or\ wasted\ in\ a\ Treatment\ Period) / (Duration\ of\ study\ drug\ exposure\ in\ the\ corresponding\ Treatment\ Period\ times\ 2)]$.

[figure not shown]
For Part B ivacaftor, compliance will be calculated as follows:

$100 \times [(Total\ number\ of\ tablets\ dispensed - the\ total\ number\ of\ unused\ tablets\ returned - the\ total\ number\ of\ tablets\ reported\ as\ lost\ or\ wasted\ in\ a\ Treatment\ Period) / (Duration\ of\ study\ drug\ exposure\ in\ the\ corresponding\ Treatment\ Period\ times\ 2)]$.

Duration of treatment and study drug compliance will be summarized by descriptive summary statistics by treatment. A separate categorical summary will be provided for the count and percent of subjects with the following compliance levels: <80% and >=80%.

1006696
Parion Sciences Incorporated
CLEAN-PCD
SAP Version 1.0

8 EFFICACY

For Part A efficacy analysis, the statistical inference will be based on change from study baseline. For Part B efficacy analysis, the statistical inference will be based on change from study baseline and change from Part B baseline. The change from study baseline will provide an assessment of the overall ivacaftor+VX-371 with and without HS effect. The change from Part B baseline will provide an assessment of additional effect of ivacaftor on top of the treatment in Part A treatment period 2 assuming that the effect of treatment in Part A treatment period 2 is stabilized by the time of ivacaftor treatment in Part B.

All Part A efficacy summaries and analyses will be based on the Part A FAS, and all Part B efficacy summaries and analyses will be based on the Part B FAS unless otherwise specified.

8.1 PRIMARY EFFICACY ENDPOINT AND ANALYSIS

Part A

The primary efficacy endpoint for Part A is the absolute change in ppFEV1 from study baseline, after 28 days of treatment in each Treatment Period of Part A.

The null hypotheses to be tested are that the mean absolute change from study baseline in ppFEV1 after 28 days of treatment is the same for 1) VX-371 in HS versus placebo; 2) VX-371 versus placebo; 3) VX-371 in HS versus HS alone. The primary assessment of efficacy will be based on the comparison of VX-371 in HS versus HS alone.

[figure not shown]
The primary efficacy analysis is based on a mixed-effects model. This model will include the absolute change from study baseline in ppFEV1 after 28 days (Visit Day 29 for Period 1 and Day 85 for Period 2) of treatment as the dependent variable, treatment and period as fixed effects, study baseline as a covariate, and subject as a random effect. The within-subject covariance will be assumed to have the compound symmetry (CS) structure. Denominator degrees of freedom for the F-test for fixed effects will be estimated using the Kenward-Roger approximation. No imputation of missing data will be done.

The estimated mean of the dependent variable, a 95% CI, and a 2-sided p-value will be provided for each treatment. There will be no adjustment for multiplicity. Similarly, the estimated between-treatment differences along with the corresponding 95% CI and 2-sided p-values will be presented.

[figure not shown]
A sample SAS code is provided below:

1006696
Parion Sciences Incorporated
CLEAN-PCD
SAP Version 1.0

Waterfall plot of the change from study baseline in ppFEV1 at Day 29 will be plotted by treatment group.

[figure not shown]

Summary statistics for the actual values and absolute changes from study baseline in pre-dose ppFEV1 will be summarized descriptively by treatment and visit based on Part A FAS.

In addition, the actual values and absolute changes at post-HS screening from pre-HS screening visit as well as actual values and absolute changes at Day 1 post-dose from Day 1 pre-dose in each period will be summarized based on Part A Safety Set and Part B Safety Set.

1006696
Parion Sciences Incorporated
CLEAN-PCD
SAP Version 1.0

[Redacted text block consisting of multiple lines of blacked-out content]

Part B

For the Part B primary efficacy endpoints, absolute changes in ppFEV1 from study baseline and from Part B baseline, after 28 days of treatment in Part B, descriptive summary statistics will be provided.

The absolute change from study baseline in ppFEV1 at Day 29 of Part B (Visit Day 113) will be analyzed using an Analysis of Covariance (ANCOVA) model with treatment as an independent variable and study baseline as well as treatment-by-study baseline interaction as covariate. The same model will be repeated using the Part B baseline instead. The LS means along with the 95% CIs and the within-treatment 2-sided P-values will be provided by treatment group. An overall estimate of the mean change across the treatment groups will also be provided with sample size for each treatment group as the weight.

Waterfall plot of the absolute change from study baseline and Part B baseline in ppFEV1 at Day 29 will be plotted by treatment group.

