## **6 STUDY OBJECTIVES**

### **6.1 Part A Objectives**

#### **Primary**

To evaluate the safety and efficacy of treatment with VX-371, administered with and without 4.2% HS, in subjects with PCD who are  $\geq 12$  years of age

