### **12.1 Sample Size and Power**

#### **Part A**

The primary efficacy objective of Part A of this study is to evaluate the efficacy of VX-371 with and without HS in subjects  $\geq 12$  years of age with PCD. For efficacy analysis, the statistical inferences will be based on change from study baseline. The null hypotheses to be tested are that the mean absolute change from study baseline in  $\text{ppFEV}_1$  after 28 days of treatment is the same

for 1) VX-371 in HS versus placebo; 2) VX-371 versus placebo; and 3) VX-371 in HS versus HS alone.

To have a feasible sample size and study duration, a crossover design has been proposed for Part A of this study. Assuming an SD of 7 percentage points, 50 subjects each for Treatment Sequence 1 and Treatment Sequence 2 are needed to have approximately 81% power to detect a 3-percentage point treatment difference in the mean absolute change in ppFEV1 from study baseline, after 28 days of treatment between VX-371 + HS and HS alone. Part A of the study will have approximately 87% power to detect a 4-percentage point change from baseline, after 28 days of treatment in ppFEV1 between VX-371 + HS and placebo. The power to detect a 3-percentage point difference between VX-371 and placebo is about 51%. The sample size estimate was based on 10000 simulation runs with an incomplete block design assuming no dropouts. In the simulation, the correlation between responses to the 2 treatments within a subject was assumed to be 0. Furthermore, a 2-sided significance level of 0.05 was used in the sample size determination with no multiplicity adjustment. The sample size also takes into consideration an assumed dropout rate of 10%.

Part A of the study will enroll approximately 150 subjects. However, as no therapeutic intervention study has previously been completed in PCD patients, the ability to enroll all 150 subjects is uncertain. Enrollment of less than 150 subjects will still provide useful information and could demonstrate an important difference between treatments. Enrollment into Part A will continue until approximately 150 subjects are randomized or the enrollment rate drops, despite suitable interventions, such that the planned enrollment cannot be achieved.

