3.5.1 Part A

The primary efficacy objective of Part A of this study is to evaluate the efficacy of VX-371 with and without HS in subjects ≥ 12 years of age with PCD. For efficacy analysis, the statistical inferences will be based on change from study baseline. The null hypotheses to be tested are that the mean absolute change from study baseline in ppFEV1 after 28 days of treatment is the same for 1) VX-371 in HS versus placebo; 2) VX-371 versus placebo; and 3) VX-371 in HS versus HS alone.

To have a feasible sample size and study duration, a crossover design has been proposed for Part A of this study. Assuming an SD of 7 percentage points, 50 subjects each for Treatment Sequence 1 and Treatment Sequence 2 are needed to have approximately 81% power to detect a 3 percentage point treatment difference in the mean absolute change in ppFEV1 from study baseline, after 28 days of treatment between VX-371 + HS

1006696
Parion Sciences Incorporated
CLEAN-PCD
SAP Version 1.0

and HS alone. Part A of the study will have approximately 87% power to detect a 4-percentage point change from baseline, after 28 days of treatment in ppFEV1 between VX-371 + HS and placebo. The power to detect a 3 percentage point difference between VX-371 and placebo is about 51%. The sample size estimate was based on 10000 simulation runs with an incomplete block design assuming no dropouts. In the simulation, the correlation between responses to the 2 treatments within a subject was assumed to be 0. Furthermore, a 2-sided significance level of 0.05 was used in the sample size determination with no multiplicity adjustment. The sample size also takes into consideration an assumed dropout rate of 10%.

Part A of the study will enroll approximately 150 subjects. However, as no therapeutic intervention study has previously been completed in PCD patients, the ability to enroll all 150 subjects is uncertain. Enrollment of less than 150 subjects will still provide useful information and could demonstrate an important difference between treatments. Enrollment into Part A will continue until approximately 150 subjects are randomized or the enrollment rate drops, despite suitable interventions, such that the planned enrollment cannot be achieved.

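### Does Part A need a pooled VX-371 contrast across the two salines, and an estimate of how the VX-371 effect differs between them?

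*SAP*

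**What the plan says.** Protocol 6.1 gives the Part A primary objective: "To evaluate the safety and efficacy of treatment with VX-371, administered with and without 4.2% HS, in subjects with PCD". Sequences 1 and 2 (50 + 50 subjects) compare VX-371 in HS with HS within subject. Sequences 3 and 4 (25 + 25) compare VX-371 in 0.17% saline with placebo within subject. Protocol 8.2.1 states that no subject crosses from one saline strength to the other.

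SAP 8.1 sets three null hypotheses, that the mean change from study baseline is "the same for 1) VX-371 in HS versus placebo; 2) VX-371 versus placebo; 3) VX-371 in HS versus HS alone". It then ranks them: "The primary assessment of efficacy will be based on the comparison of VX-371 in HS versus HS alone". For the mixed model it adds that "the estimated between-treatment differences along with the corresponding 95% CI and 2-sided p-values will be presented". For Part B the same section says that an "overall estimate of the mean change across the treatment groups will also be provided with sample size for each treatment group as the weight".

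Several places that bear on the Part A analysis cannot be read. The sample SAS code in SAP 8.1 is not visible, and a block of several lines before the Part B text is blacked out. One item in the Part A primary-endpoint row of SAP Table 2 is redacted, as is the end of the Part A text in Protocol 12.3.3.1.

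**The concern.** The objective covers VX-371 both with and without HS, and the design measures VX-371 against its own vehicle within subject in two separate groups. Yet the visible analysis uses only pairwise comparisons. Two things seem to be lost.

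- **Precision.** The 0.17% saline group carries information on VX-371 that never joins that of the HS group. Its own comparison is weak. Protocol 12.1 says: "The power to detect a 3-percentage point difference between VX-371 and placebo is about 51" percent.
- **Interpretation.** A significant result in HS beside a non-significant one in 0.17% saline invites the reading that VX-371 works only with HS. That pattern is likely even if the effects are equal. With 3 points in both, and powers of about 0.81 and 0.52, its probability is about 0.81 × (1 − 0.52) = 0.39. The direct check on that reading is the difference between the two contrasts, with its interval.

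The size-weighted overall estimate in Part B seems to show that the plan accepts summaries across the salines, which makes their absence in Part A look like an oversight.

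**Working it through.** **Inputs** (SAP 3.5.1): SD 7; 100 subjects in sequences 1 and 2 and 50 in sequences 3 and 4; 10% dropout, so 90 and 45 completers; and "a 2-sided significance level of 0.05 was used in the sample size determination with no multiplicity adjustment". On correlation: "In the simulation, the correlation between responses to the 2 treatments within a subject was assumed to be 0".

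**Step 1: reproduce the plan's power.** At correlation 0 a within-subject difference has variance 2 × 49 = 98.
- VX-371 in HS v HS: SE = 7 × √(2/90) = 1.043; power for 3 points 81.4% (plan: about 81%).
- VX-371 v placebo: SE = 7 × √(2/45) = 1.476; power for 3 points 52.3% (plan: about 51%).
- VX-371 in HS v placebo: SE = 7 × √(1/90 + 1/45) = 1.278; power for 4 points 87.7% (plan: about 87%).

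These use the non-central t distribution. All three agree with the plan to within 2 points, so the inputs are read correctly.

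**Step 2: the combined contrast.** With weights 2/3 and 1/3:

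SE = √[(2/3 × 1.043)² + (1/3 × 1.476)²] = 0.852.

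The ratio to the primary contrast is 0.852/1.043 = 0.816, which is 18% smaller. It is the same at any correlation common to both groups. With equal weights the SE is 0.904.

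**Step 3: what that buys.** The combined contrast does not measure the effect of VX-371 in HS more precisely; it measures a weighted average over two formulations. With 3 points in HS, its power depends on the effect in 0.17% saline:

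| Effect in 0.17% saline | Combined | Primary |
|---|---|---|
| 0 | 64% | 81% |
| 1 | 78% | 81% |
| 2 | 87% | 81% |
| 3 | 94% | 81% |

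Break-even: (2 × 3 + x)/3 = 3 × 0.816, so x ≈ 1.35 points.

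Correlation 0 also flatters the gain. With 3 points in both groups, the powers (combined v primary) are 98.7% v 92.7% at correlation 0.3 and 99.9% v 98.1% at 0.5. Both correlations are assumed values.

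**Step 4: the difference between the contrasts.** SE = √(1.043² + 1.476²) = 1.807. The 95% half-width is 1.978 × 1.807 ≈ 3.6 points. Power is 38% for a 3-point difference and 20% for 2 points.

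**Step 5: can the reader obtain it anyway?** The two contrasts come from different subjects, and with balanced sequences the period effect cancels within each. They are therefore close to independent. From planned output with half-widths of 1.978 × 1.043 = 2.064 and 1.978 × 1.476 = 2.919:
- difference: √(2.064² + 2.919²) = 3.575;
- combined: √[(2/3 × 2.064)² + (1/3 × 2.919)²] = 1.685.

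These equal 1.978 times the SEs in steps 4 and 2. Both quantities follow, to a close approximation, from the treatment differences and intervals that SAP 8.1 already promises.

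**The case for a change.** The strongest case for acting is that it costs almost nothing: two extra contrasts from the same model, no new data and no change to the primary test. Contrasts fixed before unblinding are worth more than the same ones worked out afterwards. Protocol 8.2.1 says the comparisons should inform the design of later studies, and whether VX-371 needs HS is such a question. The plan also warns that 150 subjects may not be reached. If 100 were randomised (an assumed figure) at the same ratio and dropout, primary power would fall to about 64%, while the combined contrast would keep about 81% if the effect is 3 points in both salines.

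The arithmetic stands, and so does the warning against comparing one p-value with another. The rest does not make a defect.

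- The gain assumes similar effects in both salines, and the difference estimate is too imprecise to check that.
- Part A already has three hypotheses without multiplicity adjustment. A fourth efficacy contrast, valued mainly for its power, would be another route to a favourable claim.
- The Part B estimate is no precedent. It averages mean change over all groups, including those without VX-371, and pools no VX-371 contrast.

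**Conclusion.** The concern does not hold. The hypotheses are pairwise, the planned contrasts test exactly those hypotheses, and none is biased or invalid for lack of a combined estimate. The objective can fairly be read as two questions, one per formulation. Protocol 8.2.1 says the design puts its power on the comparisons of greatest interest, and the 2:2:1:1 allocation favours the HS group accordingly. Nothing in the objectives or hypotheses asks for an effect averaged over salines.

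The 18% smaller standard error (0.85 against 1.04) belongs to a different quantity. It helps only if the effect in 0.17% saline exceeds about 1.35 points when that in HS is 3. Statisticians could reasonably differ on whether to report it. The difference between the contrasts would have a half-width of about 3.6 points and could not settle whether the effects are equal. A close approximation is available from the planned output.

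Nor can the omission be shown, since the SAS code and parts of the Part A analysis text are hidden, and redacted text does not count as missing.

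The figures rest on SD 7, correlation 0 unless stated, 10% dropout, balanced sequences, and equal variance in both saline groups. Subjects with data in one period only are ignored.

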### Part B

For the Part B primary efficacy endpoints, absolute change in ppFEV1 from study baseline and from Part B baseline, after 28 days of treatment in Part B, and descriptive summary statistics (n, mean, SD, SE, median, minimum, and maximum) will be provided.

The within-group *P* value and the 95% confidence interval based on normal approximation will be provided for absolute change in ppFEV1

- from study baseline, after 28 days of treatment in Part B
- from Part B baseline, after 28 days of treatment in Part B

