6 GENERAL ASPECTS FOR STATISTICAL ANALYSIS

6.1 GENERAL METHODS

All analyses will be implemented using SAS Version 9.3 or higher. Data summaries will be presented by treatment . All data will be listed.

Continuous variables will be summarized using the following descriptive summary statistics: number of subjects (n), mean, SD, median, minimum value (min), and maximum value (max).

Categorical variables will be summarized using counts and percentages. Percentages will be presented to 1 decimal place.

General rules of precision are as follows:

- Minimum and maximum values will be reported with the same precision as the reported measurement unless otherwise specified. For the calculated variables, two decimal places will be reported.
- Mean and median will be reported to 1 greater decimal place than the precision of the reported measurement unless otherwise specified.
- Standard deviation and standard error (to indicate standard error of an estimate from a statistical model) will be reported to 1 greater decimal place than the corresponding mean.
- Report p-values to 4 decimal places; report as “<0.0001”, when applicable.
- In general, the precision of mean, LS Mean, and 95% CI for a variable is the same, unless otherwise specified.

[figure not shown]

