6.2 KEY DEFINITIONS

6.2.1 Baseline

Two types of baseline will be defined for Part A. The **study baseline** is defined as the most recent nonmissing measurement (scheduled or unscheduled) collected before the first dose of study drug in the study. The definition will be applied to all demographics, background, and baseline characteristics and efficacy data analyses, including the primary endpoint analysis. The **period baseline** is defined as the most recent nonmissing measurement (scheduled or unscheduled) collected before the first dose of study drug in each Treatment Period. For Part A Treatment Period 2, the period

1006696
Parion Sciences Incorporated
CLEAN-PCD
SAP Version 1.0

baseline will be the first assessment measured after treatment-emergent (TE) period for Period 1. This definition will be applied to all safety data analyses.

For spirometry analysis in Part A, if Period 1 day 1 pre-dose data is not available, data collected at the screening visit before the test HS dose will be used as Period 1 baseline or study baseline instead of the last non-missing screening visit after the test HS dose.

For weight, height and BMI, study baseline and Period 1 baseline will be defined as the most recent non-missing measurement (scheduled or unscheduled) collected before or on the day of the first dose of study drug in Part A, Period 1. Similarly, Period 2 baseline will consider the most recent non-missing measurement (scheduled or unscheduled) collected after the TE period for Period 1 and before or on the day of first dose of study drug in Part A, Period 2.

For SGRQ and QOL-PCD, study baseline will be defined as the most recent non-missing measurement (scheduled or unscheduled) collected before or on the day of the first dose of study drug in Part A, Period 1.

For Part B, two types of baseline, study baseline and Part B baseline, will be defined. The study baseline is defined the same as study baseline for Part A. The Part B baseline is defined as the most recent non-missing measurement (scheduled or unscheduled) collected before the first dose of ivacaftor in Part B and after the last dose in Period 2.

- Change/Absolute change from study baseline in Part A and Part B will be calculated as:

post-baseline value - study baseline value.

- Change/Absolute change from period baseline in Part A will be calculated as:

post-baseline value - period baseline value.

- Change/Absolute change from Part B Baseline will be calculated as:

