8.2 SECONDARY EFFICACY ENDPOINTS AND ANALYSES

Part A

SGRQ:

1006696
Parion Sciences Incorporated
CLEAN-PCD
SAP Version 1.0

The SGRQ will have three domains (Symptoms, Activity, Impacts) and Total for age groups ≥ 16 [REDACTED]

SGRQ total score for [REDACTED] will be analyzed using similar analyses as described in [Section 8.1 Part A](#) including mixed effect model and waterfall plot. Note that the mixed effect model will use study baseline for ppFEV1 as a baseline covariate. [REDACTED]

The summary statistics for the actual values and absolute changes from study baseline will be obtained for SGRQ total score [REDACTED].

QOL-PCD:

The QOL-PCD [REDACTED] - adult version, [REDACTED]

[REDACTED]
[REDACTED]
[REDACTED]
[REDACTED] Subjects aged 18 years and older at Day 1 of Part A will complete the Adult version of the questionnaire themselves at all visits. [REDACTED]

The Lower Respiratory Symptoms domain focuses on lung symptoms and the treatments evaluated in this study are targeted toward the lungs.

QOL-PCD Lower Respiratory Symptoms domain for each QOL-PCD questionnaire version will be analyzed using similar analyses for mixed effect model and waterfall plot as described in [Section 8.1 Part A](#). Note that the mixed effect model will use study baseline for ppFEV1 as a baseline covariate. [REDACTED]

1006696
Parion Sciences Incorporated
CLEAN-PCD
SAP Version 1.0

The summary statistics for the actual values and absolute changes from study baseline will be obtained for Lower Respiratory Symptoms domain for [REDACTED] QOL-PCD questionnaire [REDACTED].

Part B

For the Part B secondary efficacy endpoint, the analysis will be based on change from study baseline as well as change from Part B baseline.

SGRQ:

[figure not shown]
SGRQ total score [REDACTED] will be analyzed using ANCOVA model and waterfall plot as described in [Section 8.1 Part B](#).

The summary statistics for the actual values and absolute changes from study baseline and changes from Part B baseline will be obtained for SGRQ total score [REDACTED].

[figure not shown]
[figure not shown]
QOL-PCD:

QOL-PCD Lower Respiratory Symptoms domain for [REDACTED] QOL-PCD questionnaire [REDACTED] will be analyzed using ANCOVA model and waterfall plot as described in [Section 8.1 Part B](#).

[figure not shown]

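### SAP Part B adjusts the change from Part B baseline for the Day 85 value, which follows randomised treatment; with LS means at the pooled Day 85 mean, a small part of any between-arm difference would appear as an ivacaftor effect

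*SAP*

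**What the plan says.** Protocol 12.3.3.1, Part B, plans a within-group P value for change in ppFEV1 from study baseline and from Part B baseline, and says "the 95% confidence interval based on normal approximation will be provided for absolute change in" ppFEV1. It names no covariate.

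SAP 8.1, Part B, replaces this with an ANCOVA of change that has "treatment as an independent variable and study baseline as well as treatment-by-study baseline interaction as covariate". It goes on: "The same model will be repeated using the Part B baseline instead". For inference: "The LS means along with the 95% CIs and the within-treatment 2-sided P-values will be provided by treatment group". An overall mean weighted by arm size is also planned, as are descriptive statistics of the unadjusted changes.

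SAP 6.2.1 defines Part B baseline as the latest non-missing value "collected before the first dose of ivacaftor in Part B and after the last dose in Period 2", in practice the Day 85 pre-dose value. SAP section 8 gives the interpretation, with reference to the Period 2 treatment and on the assumption that its effect has stabilised: "change from Part B baseline will provide an assessment of additional effect of ivacaftor on top of the treatment in Part A treatment period".

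For SGRQ and QOL-PCD in Part B, SAP 8.2 says each "will be analyzed using ANCOVA model and waterfall plot as described in" 8.1 Part B. SAP section 11 records no change from the protocol's analyses.

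**The concern.** A baseline measured before randomisation has the same expected value in every arm, so adjusting to its pooled mean does not move the arm estimates systematically. The Day 85 value is different. It is itself an outcome of Period 2 treatment, so if VX-371 or hypertonic saline (HS) works, the arms differ there in expectation. Moving every arm to one common Day 85 value then imposes regression to the mean on the arm estimates. An arm above the pooled mean is credited with a gain and an arm below it with a loss, even if nothing changes between Day 85 and Day 113.

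The P values attached to these LS means are the inference for a Part B primary efficacy endpoint, there is no arm without ivacaftor to absorb the artefact, and the SAP reads the result as ivacaftor's added effect.

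**Working it through.** **Inputs from the documents.** SD of change 7 points; VX-371 in HS versus HS 3 points; VX-371 in HS versus placebo 4 points; VX-371 versus placebo 3 points; allocation 50/50/25/25 (Protocol 12.1, Table 8-1). The first two differences imply HS versus placebo = 4 - 3 = 1 point. Part B has no sample-size calculation, so there is no Part B figure to reproduce.

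**Check of these inputs against the Part A power.** With 10% dropout (90 and 45 observations per treatment) and zero correlation, a noncentral t calculation gives 81.2%, 87.4% and 51.1%, against the stated 81%, 87% and 51%.

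**Assumptions.** The SD of 7 is carried over to the Day 85 to Day 113 change. The Day 85 between-subject SD is not in the documents. A uniform spread over the entry range 40 to 90 gives 50/√12 = 14.4; 13 and 10 are shown as alternatives. Ivacaftor has no effect and the Period 2 effect is stable, as SAP section 8 itself assumes.

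**Formula.** Write Day 85 as X = T + e1 and Day 113 as Y = T + e2, with T the subject's stable level under the Period 2 treatment. The true mean change is 0 in every arm. The within-arm slope of Y on X is b, and 1-b = SDchange² / (2 × SD85²). The slope of the change on X is therefore -(1-b), and the LS mean of an arm at the pooled Day 85 mean has expectation

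(1-b) × (arm Day 85 mean - pooled Day 85 mean).

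**Numbers.** Expected Day 85 levels relative to placebo are 4 (VX-371 in HS), 1 (HS), 3 (VX-371 alone) and 0. The pooled level is (50×4 + 50×1 + 25×3 + 25×0)/150 = 2.17. The values of 1-b are 49/(2×14.4²) = 0.118, 49/(2×13²) = 0.145 and 49/(2×10²) = 0.245.

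| Arm (all with ivacaftor) | Deviation | Shift, SD 14.4 | Shift, SD 13 | Shift, SD 10 |
|---|---|---|---|---|
| VX-371 in HS | +1.83 | +0.22 | +0.27 | +0.45 |
| HS | -1.17 | -0.14 | -0.17 | -0.29 |
| VX-371 alone | +0.83 | +0.10 | +0.12 | +0.20 |
| Placebo | -2.17 | -0.26 | -0.31 | -0.53 |

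Standard errors at full retention are about 1.0 (n = 50) and 1.4 (n = 25). Simulating 10,000 trials with the interaction model gave +0.19, -0.14, +0.11 and -0.28 at SD 14.4, with per-arm rejection of 5.3 to 5.8%. At SD 10, rejection was 5.5 to 7.6%. With 36/36/18/18 subjects (10% dropout, then an assumed 80% uptake) per-arm rejection is again about 5 to 8%. At the mild end (SD of change 4, Day 85 SD 18) 1-b is 0.025 and no shift exceeds about 0.05 points.

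**Sign.** With additive effects v (VX-371) and h (HS), the pooled level is v/2 + 2h/3. The VX-371-alone arm deviates by v/2 - 2h/3, which turns negative if h exceeds 0.75v (2.25 points at v = 3). The HS arm deviates by h/3 - v/2, which turns positive if h exceeds 1.5v (4.5 points).

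**Overall estimate.** The size-weighted deviations sum to zero, so the overall mean is unbiased (simulated -0.01). Its SE, however, uses the residual variance and treats the pooled baseline as fixed. The ratio of model SE to true SE is √(1 - (1-b)/2): 0.970 at SD 14.4 and 0.937 at SD 10. The effective cut-offs are 1.96 × 0.970 = 1.90 and 1.96 × 0.937 = 1.84, giving rejection of about 5.7% and 6.6%.

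**Unadjusted analysis.** Simple arm means are centred on zero (simulated -0.02 to 0.00). A t reference gives about 5%. The protocol's normal cut-off gives about 5.8% at n = 36 and 6.7% at n = 18.

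**The case against.** **The evaluation point is not in the SAP.** This is correct. The visible Part B text names none, and the sample code and a block just before Part B are not visible in the public copy. The pooled mean is inferred from "All analyses will be implemented using SAS Version 9.3 or higher" and the usual behaviour of LS means there. At each arm's own Day 85 mean, the shift disappears. But the covariate then changes no point estimate, so a clarifying sentence is needed either way.

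**The ppFEV1 effect is small.** This also stands. A reader might infer that a stable VX-371 effect as a whole would show up as an ivacaftor gain. Only the share 1-b of an arm's deviation leaks through, about 2 to 25% over the assumed range, and it is well below one standard error.

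**The direction is not fixed.** A reader might infer that VX-371 arms always gain and control arms always lose. With the plan's implied HS effect of 1 point they do, but a large HS effect reverses the sign in the VX-371-alone or HS arm.

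**The questionnaires may not be affected.** It is tempting to say that the distortion is much larger for SGRQ. With an assumed 4-unit VX-371 effect, no HS effect and visit correlation 0.5 to 0.7, each arm would shift by (1 - 0.5) × 2 = 1.0 to (1 - 0.7) × 2 = 0.6 units. That requires the Day 85 SGRQ score to be the covariate. SAP 8.2 names study-baseline ppFEV1 as the covariate for the Part A questionnaire models and only refers back to 8.1 for Part B, so this is unclear. Doubling the shift into a between-arm gap and setting it against the 4-unit relevance threshold would also assume a contrast that SAP 8.1 Part B does not plan.

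**The protocol's method is no better sized as written.** For per-arm ppFEV1 tests at SD 14.4 this is fair: with full arms the normal cut-off rejects 5.4 to 6.3%, against 5.3 to 5.8% for the ANCOVA. Its advantage is an unbiased estimate; correct size also needs a t reference.

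**Unadjusted descriptive statistics are planned.** They would let a reader notice a divergence, but the planned intervals and P values still come from the LS means.

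**Conclusion.** The point holds in a limited form. SAP 8.1 Part B uses a covariate measured after randomised treatment for change from Part B baseline, and it departs from the protocol's unadjusted analysis without listing this in section 11. If LS means are taken at the pooled Day 85 mean, the arm estimates carry a systematic error that is unrelated to ivacaftor. For ppFEV1 it is about 0.1 to 0.3 points at a Day 85 SD of 13 to 14.4 and up to about 0.5 at SD 10, with per-arm rejection of about 5 to 8%. The overall mean is not biased; its test rejects at about 6%.

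These sizes rest on the pooled evaluation point, the assumed Day 85 SD, an SD of change of 7, a 3-point VX-371 effect and a 1-point HS effect. The documents do not support a claim that the Part B ppFEV1 result would be seriously misleading, or that the questionnaire results are necessarily affected. The change is worth making because the error is systematic, attaches to a primary endpoint and is easy to remove.

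**What to change.** In SAP 8.1 Part B, for change from Part B baseline, take the 95% CI and P value from each arm's own unadjusted mean change and from the size-weighted overall mean, as the protocol's within-group analysis does. Use a t rather than a normal reference because the arms are small, and drop the Day 85 value as covariate.

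If the model is kept, state that LS means are evaluated at each arm's own Day 85 mean. This removes the shift, but the SE still rests on the residual variance and stays too small by the factor above, so it is second best.

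In SAP 8.2 Part B, apply the same rule to SGRQ and QOL-PCD, or name the covariate. List the departure from the protocol in SAP section 11.

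The cost is a few sentences and simpler code, with no new data. Intervals become wider by about 3% (1/0.970) to 7% (1/0.937), plus the small effect of the t cut-off, and are then correctly sized.
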